Appendix H: Referral to Burn Center***Severity Determination**

First Degree (Partial Thickness): Superficial, red, sometimes painful.

Second Degree (Partial Thickness): Skin may be red, blistered, swollen. Very painful.

Third Degree (Full Thickness): Whitish, charred or translucent, no pin prick sensation in burned area.

Percentage Total Body Surface Area (TBSA)**Burn Center Referral Criteria**

A burn center may treat adults, children, or both. Burn injuries that should be referred to a burn center include:

1. Partial thickness burns greater than 10% total body surface area (TBSA).
2. Burns that involve the face, hands, feet, genitalia, perineum, or major joints.
3. Third degree burns in any age group.
4. Electrical burns, including lightning injury.
5. Chemical burns.
6. Inhalation injury.
7. Burn injury in patients with preexisting medical disorders that could complicate management, prolong recovery, or affect mortality.
8. Any patient with burns and concomitant trauma (such as fractures) in which the burn injury poses the greatest risk of morbidity or mortality. In such cases, if the trauma poses the greater immediate risk, the patient may be initially stabilized in a trauma center before being transferred to a burn unit. Physician judgment will be necessary in such situations and should be in concert with the regional medical control plan and triage protocols.
9. Burned children in hospitals without qualified personnel or equipment for the care of children.
10. Burn injury in patients who will require special social, emotional, or rehabilitative intervention.

* Excerpted from *Guidelines for the Operation of Burn Centers* (pp. 79-86), *Resources for Optimal Care of the Injured Patient 2006*, Committee on Trauma, American College of Surgeons

APPENDIX J: DSMB QUALIFICATIONS

APPENDIX K: N-SWEAT IFU

Appendix L (for Participating Centers)

1. STATISTICAL CONSIDERATIONS AND GENERAL STATISTICAL ANALYSIS METHODS

This Statistical Analysis Plan (SAP) presents a detailed description of the statistical methods and procedures to be implemented for data analysis in the study and supersedes analyses described in the clinical investigation plan, entitled “An Evaluation of the Safety and Effectiveness of the N-SWEAT Patch for the Treatment of Primary Axillary Hyperhidrosis or Excessive Axillary Sweating (SAHARA)”. Deviations from this plan will be considered only if there is statistical justification. Any deviations from this SAP will be substantiated by sound rationale and documented in the clinical report.

This SAP also provides the analysis plan for “The pH SUB-STUDY – An Evaluation of Skin pH for a Subset of Subjects Treated in the Sahara Study”. The analysis identified for the sub-study is described in Section 13.

Categorical variables will be summarized by counts and percentages. Continuous variables will be summarized by n, mean, standard deviation, minimum, median and maximum.

When the arithmetic mean is found not to be an appropriate measure of central tendency, alternative statistics will be considered (e.g. median). When the distribution of a variable does not support the use of parametric statistics, nonparametric approaches or data transformations may be implemented. If data transformations are used, they will be specified in the final clinical report.

2. STUDY DESIGN, RANDOMIZATION AND BLINDING

The Sahara Study is a prospective, multi-center, randomized, blinded, pivotal study to evaluate the safety and effectiveness of the N-SWEAT Patch.

Subjects with primary axillary hyperhidrosis or excessive sweating (defined by a score of 3 or 4 on the HDSS), who have provided informed consent and have met the study eligibility criteria, will participate. Up to 120 adult subjects will be enrolled. The first 10 subjects will be treated with the N-SWEAT patch and constitute the roll-in cohort and up to 110 subjects will be randomized to 1 of 2 treatment groups in a 1:1 ratio to receive a single administration of the N-SWEAT Patch or a sham control patch. The randomization will be blocked by investigational center and stratified by HDSS 3 vs. 4 at baseline. Although a sample size of 100 subjects (50 in each group) is the target; up to 10 additional subjects may be enrolled to account for loss to follow up or other missing and critical data.

Randomized subjects will be blinded to their treatment assignment. Site personnel administering the treatment will observe the treatment effect and the disposal process and may be unblinded as a result of their observations. This person will not conduct the follow-up assessments and will not reveal the assumed treatment assignment to the subject, other site personnel, or the investigator at any time during the study follow-up period. Study subjects and study staff will be instructed not to discuss assumptions about the treatment received.

The sponsor will identify those who need to be unblinded in order to conduct the study. All others at the sponsor will remain blinded until the 4 week analysis.

3. COMPANION DOCUMENTS

There are two documents that are companion documents associated with this statistical analysis plan. The first is the endpoint mapping table which provides detailed information on where in the electronic data capture system the data necessary to complete the analyses specified in this plan are captured and the second is the table shell document. The table shell document is prepared for the 4 week analysis.

4. SAMPLE SIZE AND POWER CONSIDERATIONS

The primary effectiveness evaluation is driving the randomized sample size for the trial. The maximum of two scenarios considered required 50 evaluable subjects per randomized group at 4 weeks of follow-up. Increasing that number for up to 10% attrition requires 55 randomized subjects per group or 110 randomized subjects. This number provides at least 80% power for the primary efficacy objective at the two-sided 0.05 significance level.

The trial is also designed to enroll a roll-in cohort of N=10 treatment subjects at one investigational center prior to randomizing any subjects in the trial.

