8.5 Randomization Cohort

8.5.1 Randomization Process

Note: Randomization should take place immediately before treatment. If a subject meets all eligibility criteria at the screening and baseline visits; but is unable or unwilling to undergo treatment. Do not randomize. The subject should report back for randomization at the time of their planned treatment. If it is more than 7 days

CANDESANT BIOMEDICAL	CLINICAL STUDY PROTOCOL SAHARA STUDY	Document #: CB-CLP-001 Revision: E
-------------------------	---	---------------------------------------

between the qualifying baseline visit and randomization; the HDSS and the physical exam should be repeated to confirm eligibility prior to Randomization.

Randomization will be performed using an electronic system. Upon entering the subject information, the electronic system will assign a unique treatment to the subject. The subject must be treated with the assigned treatment number. In the event that the site is prevented from using the assigned treatment number (either due to the patch being missing, damaged or otherwise unusable) the site must contact the sponsor to receive an alternate treatment number assignment. A contact list will be provided for this purpose.

Subjects will be randomized 1:1 to either an active study N-SWEAT Patch (Treatment) or a sham patch (Sham). There will be no procedural difference between the Treatment Arm and the Sham Arm. The randomization will be stratified by HDSS 3 vs. 4 at baseline and blocked by investigational center. Within each HDSS stratum, block randomization with a randomly selected block size will be used. Up to 110 subjects will be randomized. At least 50 subjects randomized to each group must be evaluable for the primary efficacy endpoint. Up to 10 additional subjects may be enrolled to account for loss to follow up or other missing and critical data.

Crossovers are not permitted by this protocol. Subjects may only receive the N-SWEAT Patch if they are randomized to do so.

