11. EFFICACY ANALYSIS

11.1 Primary Efficacy

The proportion of subjects with HDSS of 1 or 2 at 4-weeks in subjects randomized to treatment (p_T) will be higher than that in subjects randomized to sham (p_S).

Subjects Included in Analysis: All ITT subjects.

Endpoint(s): The proportion of subjects with HDSS of 1 or 2 at 4 weeks of follow-up.

Hypothesis:

H_0 : The proportion of subjects with HDSS of 1 or 2 at 4-weeks in subjects randomized to treatment (p_T) will be lower than or equal to that in subjects randomized to sham (p_S), $p_T \leq p_S$

H_a : The proportion of subjects with HDSS of 1 or 2 at 4-weeks in subjects randomized to treatment (p_T) will be greater than that in subjects randomized to sham (p_S), $p_T > p_S$

Sample Size Rationale: . The sample size and power calculations for the randomized cohort are based on the company's clinical trial data as well as on published data (Glaser et al., 2012). To account for substantial variability in the proportion of responders across various trials, multiple scenarios were considered.

Per definition of the primary endpoint a responder is a patient with HDSS values of 1 or 2 at 4-weeks post treatment. If proportions of responders in the treated vs. sham arms are 85% vs. 60%, respectively, then using PASS 2019, testing two proportions using the Mantel-Haenszel test, 50 patients per arm will be needed to detect the treatment difference with the 80% power at the 0.05 two-sided significance level. If proportions of responders in the

treated vs. sham arms are 73% vs. 44%, then 45 patients per arm will be needed. The evaluable sample size of 50 patients per arm was chosen

Primary Statistical Analysis: The proportion of patients with HDSS of 1 or 2 at 4 weeks post-treatment will be compared between treatment vs. sham using the Cochran-Mantel-Haenszel (CMH) test stratified by baseline HDSS value of 3 vs. 4 in the FAS population. Statistical significance is achieved with two-sided p-value <0.05 equivalent to one-sided p-value < 0.025.

Additional Statistical Analysis: Additional analyses include those summarized in **Section 8.3** Evaluation for Pooling of Data and **Section 9** Handling of Missing Data for the Primary Efficacy Endpoint. The primary statistical analysis will be completed in the PP population as well.

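### The inflation from 50 evaluable to 55 randomised per group covers about 9% attrition, not the stated 10%; the power claim is unaffected

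*SAP*

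**What the plan says.** SAP 4 gives the starting point: "The maximum of two scenarios considered required 50 evaluable subjects per randomized group at 4 weeks of follow-up". It then adds the allowance for loss: "Increasing that number for up to 10% attrition requires 55 randomized subjects per group or 110 randomized subjects". It closes with the power claim: "This number provides at least 80% power for the primary efficacy objective at the two-sided 0.05 significance level". Protocol 9.3 carries the same reasoning and the same figures.

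The 50 comes from the larger of two scenarios in SAP 11.1 (also Protocol 9.10.1). The first is "If proportions of responders in the treated vs. sham arms are 85% vs. 60%, respectively", for which "50 patients per arm will be needed to detect the treatment difference with the 80% power at the 0.05 two-sided significance level". In the second, "treated vs. sham arms are 73% vs. 44%, then 45 patients per arm will be needed".

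Randomisation is capped. SAP 2 says "up to 110 subjects will be randomized to 1 of 2 treatment groups in a 1:1 ratio", and the same ceiling of 110 appears in the Protocol synopsis and in Protocol 7.1, 8.5.1 and 9.2. The overall enrolment figure of 120 in SAP 2 and Protocol 9.2 includes the 10 roll-in subjects, so it holds no randomised reserve.

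What the 110 must deliver is described in three ways:

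- **Evaluable.** Protocol 8.5.1: "At least 50 subjects randomized to each group must be evaluable for the primary efficacy endpoint".
- **Treated.** The Protocol synopsis and Protocol 7.1 ask only that at least 50 per group receive the patch.
- **Target.** SAP 2 calls 100 subjects, 50 per group, the target, with up to 10 more to cover loss and missing data.

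**The concern.** An attrition allowance answers the question of how many must be randomised so that enough remain after the stated loss. Since the loss is a share of those randomised, the required number is the evaluable number divided by one minus the loss. Multiplying by one plus the loss gives a smaller number that does not quite return the evaluable target.

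Two things depend on this. The 10% is a stated design tolerance, and someone monitoring retention would take it to mean that losses up to that level leave the plan intact. And Protocol 8.5.1 makes 50 evaluable per group a requirement in the same paragraph that caps randomisation at 110. If the allowance is slightly too generous, the requirement is missed slightly before the stated limit is reached.

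**Working it through.** **Inputs.** Two-sided alpha 0.05; power 80%; 1:1 allocation; responder rates 85% vs 60% and 73% vs 44%; 50 and 45 per arm (SAP 11.1); 50 evaluable per group, up to 10% attrition, 55 per group and 110 in total (SAP 4, Protocol 9.3).

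**Step 1: reproduce the evaluable sample size.** The normal-approximation formula with pooled variance under the null is

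n = [1.960 × √(2p̄(1−p̄)) + 0.842 × √(p₁(1−p₁) + p₂(1−p₂))]² / (p₁−p₂)²

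- 85% vs 60%: p̄ = 0.725. The numerator root is 1.960 × √0.39875 + 0.842 × √0.3675 = 1.748. Then (1.748/0.25)² = 48.9, so 49 per arm (stated: 50).
- 73% vs 44%: p̄ = 0.585. The numerator root is 1.960 × √0.48555 + 0.842 × √0.4435 = 1.926. Then (1.926/0.29)² = 44.1, so 45 per arm (stated: 45).

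Both stated figures are reproduced to within one subject. The 50 is sound.

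**Step 2: reproduce the inflation.** 50 × (1 + 0.10) = 55 per group, and 2 × 55 = 110. This is exactly the plan's figure, so the plan multiplied.

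**Step 3: check it against its own premise.**

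- Division: 50/(1 − 0.10) = 55.6, which is above 55.
- Expected evaluable at 10% loss: 55 × 0.90 = 49.5 per group, and 110 × 0.90 = 99 in total. Two groups of 50 need 100.
- Loss that 55 per group can absorb: 1 − 50/55 = 5/55 = 9.1%.
- Check at 9%: 55 × 0.91 = 50.05, which meets 50.

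**Step 4: does the power claim survive a full 10% loss?** Exact power comes from enumerating all outcomes of two binomials, using the Mantel-Haenszel statistic with its N−1 variance, in a single stratum, two-sided 0.05. The normal approximation is the formula in Step 1 solved for power.

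| Scenario | Exact, 49 per arm | Normal approximation, 49 per arm | Normal approximation, 49.5 per arm |
|---|---|---|---|
| 85% vs 60% | 80.9% | 80.1% | 80.5% |
| 73% vs 44% | 84.5% | 84.1% | 84.4% |

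For comparison, exact power at 50 per arm for 85% vs 60% is 81.8%. Every entry is at or above 80%.

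**The case against.** The strongest reply is that this is a rounding-sized matter. The shortfall is half a subject per group, it arises only at the upper end of an allowance worded as a maximum, and it disappears at 9.1% loss or less. One could also read the 10% as a margin on the evaluable target: SAP 2 describes 10 subjects on top of 100, which is 10% in that sense. Most of this stands. The size is trivial, and no analysis, error rate or conclusion changes. What does not stand is the sentence as written: it names attrition, and a 10% loss from 55 does not leave 50.

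Three stronger readings are tempting, and the documents support none of them.

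- **The trial is underpowered.** It is not. Step 4 shows at least 80% power at 49 per arm in both scenarios.
- **The cap and the evaluable requirement contradict each other.** They fail to fit only between about 9.1% and 10% loss, and only under the wording of Protocol 8.5.1. The treated wording in the synopsis and Protocol 7.1 is met by 55 randomised per group when losses come after treatment, and SAP 2 speaks only of a target. SAP 1 says the SAP supersedes the protocol's analyses, which does not clearly extend to an enrolment requirement, so the wordings remain unreconciled.
- **The plan should guarantee 50 evaluable per group, so more must be randomised.** The actual number lost will vary by chance around whatever rate is assumed. No inflation based on the expected loss removes that variation, and rounding 55.6 up would not either.

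**Conclusion.** The point holds as a small arithmetic correction. SAP 4 and Protocol 9.3 state a tolerance of 10% where the sample size delivers 9.1%. At the full 10%, the expected count is 49.5 evaluable per group (99 in total) against the 50 that Protocol 8.5.1 asks for. The power statement stands in both scenarios.

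This rests on three assumptions: attrition is a proportion of those randomised, losses fall about equally on the two groups, and the stated responder rates apply without differing between the two baseline HDSS strata. The more useful by-product is that the documents do not agree on whether the 50 per group are to be evaluable, treated or merely aimed for.

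**What to change.** 1. In SAP 4 and Protocol 9.3, keep 55 per group and 110 in total, and change the allowance from up to 10% to up to 9% attrition.
2. Choose one meaning for the 50-per-group requirement (evaluable, treated or target) and use it in the Protocol synopsis, Protocol 7.1, Protocol 8.5.1 and SAP 2.

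The first change is one figure in two sentences. It leaves the design, the cap and the power statement alone, and its only price is a slightly less favourable stated tolerance. The second is a wording change in up to four places.

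Raising the randomised number is not worth it. It would mean enrolling more subjects and revising the 110 ceiling, the allowance of 10 additional subjects and the 120 total wherever they appear, in order to protect a power claim that already holds.

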5. STUDY SUCCESS

The Sahara study will be deemed a success with a statistically significantly higher (at the 0.05 two-sided significance level) proportion of patients with HDSS score of 1 or 2 at 4 weeks post-treatment in subjects randomized to treatment vs. sham (primary effectiveness endpoint) accompanied by an acceptable safety profile.

6. ANALYSIS SETS / POPULATIONS

6.1 Roll-in Cohort

The roll-in cohort is an initial cohort of N=10 active treatment subjects enrolled at one investigational site to provide FDA with an initial assessment for safety of the device. Efficacy endpoints for roll-in subjects will be restricted to summary statistics and reported separately..

6.2 Intent-to-Treat Population

The intent-to-treat (ITT) population will include all randomized patients assigned to treatment. In this population, treatment will be based on the treatment to which patients were randomly assigned regardless of which treatment they actually received.

6.3 Safety Population

The safety population is the ITT population plus the roll-in cohort.

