6. STUDY ENDPOINTS

6.1 Safety Assessment

Safety will be confirmed by an assessment of the occurrence of local skin reactions, treatment-related AEs and SAEs for all subjects treated with the N-SWEAT device. Local skin reactions are defined by the criteria shown in **Appendix B**. AE and SAEs are defined in **Section 10** of this protocol.

Safety data from the roll-in cohort will be compiled and analyzed after all 10 subjects have completed 2-week and 4-week follow-up. Safety data from the roll-in cohort and the randomized cohort will be pooled.

After the 30th, 60th, and 90th subject from the randomized cohort (active and control) is treated and followed for 7 days, the running safety report will be submitted to FDA. The report will be submitted within 30 days of treatment.

The interval safety report will include:

1. Cumulative frequency tables of all AE reported to date for the active patch, and all the AE reported to date for the sham patch, using the terminology in Table 9; and
2. A list of AEs in the recently completed 30-subject cohort, to include the device used (active or control), time to onset, time to resolution, intervention (including OTC product use), whether the AE was procedure- or device-related, and descriptive and photographic data.

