9.5.4 Modified Intent-to-Treat and Full Analysis Set

The modified intent to treat (mITT) will include all randomized patients in the ITT population who were exposed to randomized treatment. The full-analysis set (FAS) is those mITT subjects that have evaluable data for the endpoint.

The mITT population, like the ITT population, will include all randomized patients assigned to treatment regardless of which treatment they actually received. However, unlike the ITT population, the mITT population excludes patients who are randomized but fail to initiate treatment (treatment or control patch).

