10. PRIMARY SAFETY ANALYSIS

Subjects Included in Analysis: All subjects in the Safety Population.

Endpoint(s): Local skin reactions and adverse events.

Hypothesis: A single hypothesis test associated with a specific safety endpoint is not being proposed for the primary safety outcome. Rather, the local skin reaction and adverse event profile in total will be reviewed for acceptability.

Primary Statistical Analysis: Number and percent of subjects affected by each DSMB classified event or reaction will be summarized. Subgroups of events/reactions will also be summarized and include but are not limited to serious events, those related to the treatment, and those that are both serious and related to the treatment. Events will additionally be summarized by DSMB determined severity and investigator reported time required for resolution. Treatment related AEs are defined by either a possible, probable, or highly probable relationship to the N-SWEAT Patch or possible, probable, or highly probable relationship to the N-SWEAT Procedure as adjudicated by the DSMB.

Lastly, adverse events will be summarized in subgroups defined by total time of treatment over both axilla, average and maximum pain throughout treatments. Subgroups will be defined by above and below the median for each treatment characteristic.

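### The safety population is the ITT set plus roll-in, so untreated subjects stay in the adverse event denominators; no by-patch-received rule and no roll-in column are specified

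*SAP*

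**What the plan says.** SAP 6.3 defines the set in one sentence: "The safety population is the ITT population plus the roll-in cohort". Protocol 9.5.3 is identical. SAP 10 runs the primary safety analysis on "All subjects in the Safety Population".

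The ITT set is all randomised patients, and SAP 6.2 adds: "In this population, treatment will be based on the treatment to which patients were randomly assigned regardless of which treatment they actually received". Neither document gives a separate attribution rule for safety.

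Protocol 9.5.4 recognises that a randomised subject may go untreated, since "the mITT population excludes patients who are randomized but fail to initiate treatment". The SAP has no mITT set.

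On roll-in, SAP 6.1 says: "The roll-in cohort is an initial cohort of N=10 active treatment subjects enrolled at one investigational site". Protocol 6.1 says: "Safety data from the roll-in cohort and the randomized cohort will be pooled". The same section describes safety as assessed "for all subjects treated with the N-SWEAT device". The protocol synopsis promises safety summaries by treatment group and for all patients. SAP 10 does not say how roll-in subjects are to be displayed.

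**The concern.** A safety table should show how often events occurred among people exposed to each device. A set built on ITT can miss this in two ways: an untreated subject adds to the denominator but cannot have a device event, and a subject given the other patch has events shown under a device they did not receive.

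Roll-in raises a different issue. These 10 subjects all receive N-SWEAT, at one site, before randomisation opens, and blinding is described only for the randomised cohort. No sham subjects match them. If they sit in the N-SWEAT column, the difference from sham mixes device with site, period and knowledge of treatment. That matters for descriptors reported by the subject, such as burning, stinging and itching (Protocol Appendix B).

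Study success requires an acceptable safety profile as well as the primary efficacy result (SAP 5). No safety hypothesis is tested (SAP 10), so these descriptive tables are the safety evidence.

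**Working it through.** **1. Size of the set.** Neither document gives a numerical figure for the safety analysis beyond enrolment. Up to 110 are randomised 1:1, so 55 per arm (SAP 4), with 10 roll-in subjects. The set is 110 + 10 = 120, matching the enrolment ceiling in SAP 2. If roll-in is merged, N-SWEAT has 55 + 10 = 65 and sham has 55.

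**2. Can a randomised subject be untreated?** Yes. Protocol 8.7.1 calls for a final skin inspection after the pre-randomisation check and tells the operator not to treat if the site fails it. Protocol 8.10 lists ineligibility for treatment as a withdrawal reason, and Protocol 9.5.4 provides for such subjects. SAP 10 also splits adverse events by treatment time and pain during treatment, which do not exist for a subject with no patch.

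**3. Which basis does each safety output use?**

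| Output | Basis |
|---|---|
| Safety assessment, Protocol 6.1 | subjects treated with N-SWEAT |
| Interval reports, SAP 7 and Protocol 6.1 | active or sham patch; device used |
| Stopping rule after 10 subjects, Protocol 11.5 | subjects treated with N-SWEAT |
| Final safety tables, SAP 6.3 and 10 | ITT plus roll-in; only the ITT attribution rule is available |

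The final tables are the exception. An interval report and the final report could place the same subject under different devices.

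**4. Dilution from untreated subjects.** The documents give no count, so u is assumed to run from 0 to 5 of the 55 assigned to N-SWEAT, with no events among them. The displayed rate is r × (65 − u)/65, a relative understatement of u/65. For r = 10% (assumed):

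| u | Displayed rate | Relative loss, pooled 65 | Relative loss, randomised 55 (u/55) |
|---|---|---|---|
| 0 | 10.0% | 0% | 0% |
| 1 | 9.8% | 1.5% | 1.8% |
| 2 | 9.7% | 3.1% | 3.6% |
| 3 | 9.5% | 4.6% | 5.5% |
| 5 | 9.2% | 7.7% | 9.1% |

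**5. Wrong patch.** One sham-assigned subject who received N-SWEAT and had an event would add 1/55 = 1.8 percentage points to the sham column if counted by assignment.

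**6. Roll-in, if merged.** Its share is 10/65 = 15.4% (10/60 = 16.7% with 50 randomised per arm). Assume a randomised device rate of 10% and x of the 10 roll-in subjects with an event. The merged rate is (55 × 0.10 + x)/65:

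| x | Merged rate |
|---|---|
| 0 | 8.5% |
| 1 | 10.0% |
| 2 | 11.5% |
| 3 | 13.1% |
| 5 | 16.2% |

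The shift can go either way, so merging is not reliably conservative.

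**The case against.** - **Attribution is inferred.** The assigned-arm sentence in SAP 6.2 is about the ITT population; SAP 6.3 says only who is in the safety set. A reader might infer that the plan expressly orders safety to be tabulated by assigned arm. It does not. But it offers no other rule, and the SAP supersedes the protocol's analyses (SAP 1), so an analyst following it would have only the ITT rule to apply.
- **Untreated or wrongly treated subjects should be rare.** Randomisation comes just before treatment, subjects unable or unwilling to be treated are not randomised, and crossover is barred (Protocol 8.5.1). Replacement treatment numbers come from the sponsor, and nothing says they may change the arm. This stands and limits the size.
- **Merging is not established.** A reader might conclude that the sham comparison is not randomised. The documents do not go that far. SAP 10 does not mention pooling; SAP 8.1 and 8.2 name roll-in as its own group for other tables; the protocol's pooling could mean the all-patients total; and the layout may be settled in the table shell document (SAP 3), which is not available here. Roll-in safety is also summarised early on its own (SAP 7; Protocol 6.1). That does not guarantee a separate column in the final tables.
- **Protocol 6.1 is not an analysis-set definition.** Read literally it would leave out sham subjects. It is a mismatch of basis, not a formal contradiction.
- **No test is planned.** Type I error and power are untouched. This stands, though the descriptive rates still carry the safety judgement.

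**Conclusion.** The point holds in a limited form. The stated definition keeps randomised but untreated subjects in the denominators, and the only attribution rule available would place a wrongly treated subject under the assigned arm. Neither matches the treated or device-used basis of the other safety outputs. The numerical effect is probably small and may be zero: about 1.5% relative per untreated N-SWEAT subject in a pooled group of 65, and 7.7% if there were five, a number assumed only to show the range.

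The roll-in part is conditional. If those 10 subjects are merged into the N-SWEAT column, 15.4% of it is non-randomised and the displayed contrast with sham is no longer a randomised one. If they have their own column, the problem does not arise. The SAP should settle this before the sponsor is unblinded at the 4-week analysis. Including roll-in subjects in an overall device rate is reasonable and is not at issue.

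**What to change.** - Redefine the safety population in SAP 6.3 and Protocol 9.5.3 as all subjects to whom a patch was applied, analysed by the patch actually received.
- State in SAP 10 that adverse event and skin reaction tables show randomised N-SWEAT, randomised sham and roll-in in separate columns, plus a total for all N-SWEAT-treated subjects. The total keeps the pooling that Protocol 6.1 calls for.
- State that any N-SWEAT versus sham comparison of safety uses the randomised columns only.

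The cost is SAP wording, the matching protocol sentence and an extra table column. Sample size, data collection and the efficacy analysis do not change.
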